## 19.0 RECORDS

### 19.1 Case Report Forms (CRFs)

Electronic case report forms will be used in this study. The Investigator must ensure that the clinical data required by the study protocol are carefully reported in English in the eCRF. He/she must also check that the data reported in the eCRF correspond to those in the official files (source documentation).

Before the start of clinical activities an agreement will be completed and signed by the Investigator and the Sponsor/CRO, to summarise the source of data captured in the eCRF, specifying those data that will be recorded directly into the eCRF (i.e. for which there will be no prior written or electronic record of data).

ECG measurement results must be printed and signed by the Investigator and kept as source data on site after entering into the eCRF. The investigator will receive the results from the local laboratory by means of a laboratory report: this report should be signed by the investigator, stored as source and a copy should be present in the patient's file.

All other data has to be documented in the patient file as source data first and then entered into the eCRF.

Data must be entered into eCRFs in English by the designated site personnel as soon as possible after a patient visit, and monitors will have access to data recorded. These data will be reviewed versus source documents by trial monitors for completeness and acceptability during monitoring visits. Any correction to the eCRFs' entries must be carried out by the Investigator or a designated member of staff. Corrections are recorded in an audit trail that records the old information, the new information, and identification of the person making the changes, date of correction made and reason for change. In the interests of completeness of data acquisition, the questions which are repeated in each section of the eCRFs should be answered in full, even if there are no changes from a previous examination. A reasonable explanation must be given by the Investigator for all missing data. The Investigator or his/her designees named in the clinical staff list will review the eCRF for accuracy and completeness. The Investigator must electronically sign and date the eCRF pages as indicated.

### 19.2 Records Maintained by the Investigator

A copy of all trial records (any documents sent or received from the Sponsor/CRO, correspondence with EC and any other institution or authority and relevant approvals, patients' source data and patients' identification documentation) must be maintained by the

Investigator for at least 5 years, or for a longer period, where so required by other applicable requirements or by an agreement between the Sponsor and the Investigator.

### **19.3 Trial Master File**

The Trial Master File (TMF) will be maintained electronically by the CRO according to the respective CRO SOPs with direct access for all study participants.

At the end of the trial, the TMF will be transferred to the Sponsor, where it will be archived according to specific Sponsor SOPs. A copy of the Investigator files will be left on site after trial end.

### **19.4 Trial Monitoring**

The trial will be monitored by means of regular visits and telephone calls according to specific and pre-defined SOPs and trial specific monitoring guidelines. Details of the visits will be recorded in appropriate Monitoring Report forms to be submitted regularly to Sponsor. Any relevant protocol deviation must be promptly communicated to designated Sponsor's personnel.

Monitoring will be performed by personnel of the CRO.

### **19.5 Confidentiality of Subject's Information**

The Investigator has the responsibility to maintain the pseudonymity of patients in compliance with the applicable data protection law. In all study documents, patients are associated to a code which does not reveal the patient's identity. Only at the site, the Investigator will hold the patient's identity on a Subject Identification Form under his/her responsibility.

The site and the Sponsor shall process personal data of patients involved in the clinical study as Data Controllers and in compliance with the applicable data protection laws, each of them in its area of competence and in accordance with the responsibilities provided by GCP, only in relation to the study performance and for pharmacovigilance purposes. The Investigator will maintain this for the longest period allowed by his/her own institution and, in any case, until further communication from the Sponsor.

Any contracted organisation either as Data Processor including the CRO, the local laboratory and ITRS provider, will act in compliance with the term and conditions agreed with the Sponsor.

## **20.0 BIOMETRICS**

### **20.1 Data Handling**

A data management plan specifying all relevant aspects of data processing for the study (including data validation, cleaning, correcting, and releasing) will be maintained and stored at PAREXEL.

Electronic systems that may be used to process and/or collect data in this study will include the following:

- ITRS system – randomization, study drug supply

- eCRF and Electronic Data Capture (EDC) system – data capture
- Statistical Analysis System (SAS®) – statistical review and analysis
- Pharmacovigilance safety database

Subject data will be captured in an eCRF system and reviewed by the Clinical Research Associate in order to check CTP adherence and to detect any data inconsistency or discrepancy (data validation step).

Medical/surgical history and underlying diseases and AEs will be coded using the Medical Dictionary for Regulatory Activities (MedDRA) latest version current at trial start and which will be updated at each release of a new version during the trial.

Previous and concomitant medications will be coded using the World Health Organization-Drug Dictionary (WHO-DD). Actual versions of coding dictionaries used will be stated in the CTR.

The final data file will be transferred to the Sponsor in the agreed format as soon as possible after the trial is completed.

## 20.2 Endpoints

### 20.2.1 Primary Endpoint

The primary efficacy endpoint of this study is the change from baseline to week 16 in the mean total daily “OFF” time, as assessed by 24-hour patient diary cards, of safinamide 100 mg/day compared to placebo, given as add-on therapy in PD patients with motor fluctuations on stable doses of L-dopa.

### 20.2.2 Secondary Endpoints

The key secondary efficacy endpoint of this study is:

- The change from baseline to week 16 in pain severity, as assessed by an 11-point Numerical Rating Scale (NRS).

Other secondary efficacy endpoints of this study are:

- The change from baseline to week 16 in the mean total daily “ON” time, as assessed by 24-hour patient diary cards.
- The change from baseline to week 16 in the mean daily “ON” time with no/non-troublesome dyskinesia, as assessed by 24-hour patient diary cards.
- The change from baseline to week 16 in the UPDRS total score during the “ON” phase.
- The change from baseline to week 16 in the UPDRS part II (ADL) score during the “ON” phase.
- The change from baseline to week 16 in the UPDRS part III (motor function) score during the “ON” phase.
- The CGI-S score at week 16.
- The change from baseline to week 16 in the CGI-C.

- The change from baseline to week 16 in the PDQ-39 score.

### **20.2.3 Safety Endpoints**

The safety endpoints for this study are:

- The nature, frequency, severity, relationship (to study drug), actions taken, and outcome of treatment-emergent adverse events (TEAEs) and treatment-emergent serious adverse events (TSAEs).
- Physical examination findings (clinically significant).
- Vital sign (heart rate, systolic and diastolic blood pressure) values, including occurrence of abnormalities.
- 12-lead electrocardiogram (ECG) parameter measures, including occurrence of abnormalities
- Clinical chemistry and haematology values, including shifts from baseline and occurrence of abnormalities.

## **20.3 Sample Size**

Sample size was computed through a Monte Carlo study with 1000 runs and using a Fixed Sequence Procedure (25) to account for multiplicity over the study primary endpoint (change from baseline to week 16 in the mean total daily “OFF” time) and the key secondary endpoint (change from baseline to week 16 in pain severity, as assessed by an 11-point Numerical Rating Scale - NRS). The Fixed Sequence Procedure implies that the key secondary endpoint will be testable provided that the primary endpoint has achieved statistical significance with a two-tailed p-value  $\leq 0.05$ .

Based on the Monte Carlo simulation it was estimated that a total sample size of 260 patients (130 in the safinamide and 130 in the placebo groups) ensures 90% power to detect a mean difference in the ‘off’ time at least 0.9 h between the safinamide and placebo groups with a two-sided significance level (alpha) of 0.05 using a two-sample t-test and assuming standard deviations of 2.35 for safinamide and 2.06 for placebo. Effect size and standard deviation estimates used in sample size computations are gathered from the Settle Statistical Report (Table 15.2.13).

Moreover, the same Monte Carlo study showed that the total sample size of 260 patients would also permit a marginal power equal to 88% to detect 1 point treatment difference in the NRS between the safinamide and placebo groups with a two-sided significance level (alpha) of 0.05 using a two-sample t-test and assuming a pooled standard deviations of 2.0. Standard deviation was estimated on the basis of previous post-hoc analyses of pain (25) whilst a 1 point treatment difference is considered to be a clinically meaningful treatment effect (26).

Assuming an attrition rate equal to 15% a total of approximately 306 patients will be randomized (153 in the safinamide and 153 in the placebo groups). The sample size calculations were performed using the Mediana package (27).

## **20.4 Statistical Analyses**

### **20.4.1 General Statistical Considerations**

All data captured on eCRFs will be available as listings.

The statistical analysis will be performed by the CRO. If not otherwise stated all statistical analyses and data tabulations will be produced using SAS® for Windows release 9.4 (64-bit) or later (SAS Institute Inc., Cary, NC, USA).

Unless stated otherwise, all available data from withdrawn subjects will be included in the analysis up to the time of withdrawal.

The primary study objective will be assessed by testing the superiority of Safinamide compared to placebo and will be achieved if the analysis on primary end-point will be found statistically significant. The key secondary objective will be always assessed through a superiority analysis of Safinamide compared to placebo and, similarly, will be reached if the analysis on key secondary end-point will be found statistically significant. Conversely, the analyses on the remaining secondary efficacy endpoints will be treated as non-key secondary objectives since they will be performed only to support primary endpoints findings.

All tests will be two-sided and performed at the significance nominal level of  $\alpha = 0.05$ . Details are reported in Section 20.4.5.

#### ***20.4.2 Trial Populations***

There will be 4 analysis populations defined for the trial analyses:

##### Randomized Population

The Randomized Population will include all subjects who provided informed consent and received a patient number (randomisation number) whether or not they receive IMP.

##### Full Analysis Set

The Full Analysis Set (FAS) will comprise all patients who provided informed consent, were randomized and received at least 1 dose or partial dose of the IMP.

Primary analyses will be performed on the FAS population with exclusions from the randomized defined and justified in the SAP.

Following the randomized principle, patients will be analyzed according to the treatment they have been assigned to at the randomization.

The FAS will be used to produce summaries of baseline patient characteristics and for the analysis of all efficacy endpoints.

##### Safety Population

The Safety Population will comprise all patients who provide Informed Consent and received at least 1 dose or partial dose of IMP.

Patients will be analyzed according to the treatment they actually received.

The Safety Population will be used to produce summaries of all safety related endpoints and demography.

##### Per-protocol Population

The Per-protocol Population (PP) will include all FAS patients who were compliant with study drug administration had no major protocol deviations that were considered as potentially impacting the efficacy results. Major protocol deviations might include, but are not be limited to, patients taking a not-permitted concomitant medication, the IMP not being

administered during the trial as defined in the protocol, patients receiving a treatment different than the one assigned by randomization; others will be defined in the SAP.

Results of the primary and secondary efficacy endpoints analyses conducted in the PP will be considered as supportive.

Exclusion of patients from the PP analyses will be decided jointly by the CRO and Sponsor's Medical Monitor, Clinical Trial Manager and Statistician prior to unblinding of the randomization code and database release.

The patients or observations to be excluded, and the reasons for their exclusion will be documented and approved by the above mentioned persons prior to database release. The documentation will be filed together with the remaining trial documentation.

The number of patients in each analysis population will be reported. Violations excluding patients from any particular population will be described, reporting the number of protocol violators per each criterion. All protocol violations, minor ones included, will be listed.

#### **20.4.3 Efficacy Data**

The FAS population will be used for the primary analyses of each of the efficacy endpoints whilst results from supplemental analyses using the Per Protocol Population will be compared to those based on the FAS population to assess the effects of dropouts, missing data, protocol violations and deviations.

The distributions of all the efficacy endpoints listed in Section 20.2 will be summarized by treatment group and time point. Counts and percentages will be reported with the latest computed based on the numbers of patients with non-missing observations. The percentages will be suppressed when the count is zero in order to draw attention to the non-zero counts. Furthermore, efficacy endpoints will be further summarized by arithmetic means, standard deviations, medians quartiles, minima and maxima.

##### **20.4.3.1 Analysis of Primary Endpoint**

The primary objective of the study is to evaluate the change from baseline to week 16 in the mean "OFF" time, as assessed by the 24-hour patient diary, of safinamide 100 mg/day compared to placebo, given as add-on therapy in PD patients with motor fluctuations on stable doses of L-dopa. The analysis of primary efficacy parameter will be done using an analysis of co-variance (ANCOVA) with treatment and centre as independent factor, baseline mean "OFF" time measurement as covariate and change from baseline as dependent variable. Results will be reported as Least-Square Means for treatment differences with associated two-tailed 95% confidence intervals and corresponding two-sided p-values.

The main time point for comparison between treatment groups is week 16, but other available measurements at other visits will be analysed as well.

##### **20.4.3.2 Analysis of Key Secondary Endpoint**

The key secondary objective of the study is to evaluate the change from baseline to week 16 in pain severity, as assessed by an 11-point Numerical Rating Scale (NRS), of safinamide 100 mg/day compared to placebo. As for the analysis of the primary endpoint, the analysis of key secondary efficacy parameter will be done using an analysis of co-variance (ANCOVA) with treatment and centre as independent factor, baseline NRS measurement as covariate and change from baseline as dependent variable. Results will be reported as Least-Square Means

for treatment differences with associated two-tailed 95% confidence intervals and corresponding two-sided p-values.

The main time point for comparison between treatment groups is week 16, but other available measurements at other visits will be analyzed as well.

#### **20.4.3.3 Analyses of Other Secondary Endpoints**

- Change from baseline to week 16 in the mean total daily “ON” time, as assessed by 24-hour patient diary cards: the hypothesis of superiority of safinamide compared to placebo will be assessed using an ANCOVA model parameterized as above (i.e. as for the primary and key secondary endpoint), with point estimate of treatment differences reported as Least-Square Mean with associated two-tailed 95% confidence intervals and two-sided p-value.
- Change from baseline to week 16 in the mean daily “ON” time with no/non-troublesome dyskinesia, as assessed by 24-hour patient diary cards: the hypothesis of superiority of safinamide compared to placebo will be assessed using an ANCOVA model parameterized as above, with point estimate of treatment differences reported as Least-Square Mean with associated two-tailed 95% confidence intervals and two-sided p-value.
- Change from baseline to week 16 in the UPDRS total score during the “ON” phase: the hypothesis of superiority of safinamide compared to placebo will be assessed using an ANCOVA model parameterized as above, with point estimate of treatment differences reported as Least-Square Mean with associated two-tailed 95% confidence intervals and two-sided p-value..
- Change from baseline to week 16 in the UPDRS part II (ADL) score during the “ON” phase: the hypothesis of superiority of safinamide compared to placebo will be assessed using an ANCOVA model parameterized as above, with point estimate of treatment differences reported as Least-Square Mean with associated two-tailed 95% confidence intervals and two-sided p-value.
- Change from baseline to week 16 in the UPDRS part III (motor function) score during the “ON” phase: the hypothesis of superiority of safinamide compared to placebo will be assessed using an ANCOVA model parameterized as above, with point estimate of treatment differences reported as Least-Square Mean with associated two-tailed 95% confidence intervals and two-sided p-value.
- CGI-S score assessed at week 16: the hypothesis of superiority of safinamide compared to placebo will be assessed using the Wilcoxon-Mann-Whitney test stratified by centre, whilst point estimate of treatment differences will be reported as Hodges-Lehmann estimators together with associated two-sided nonparametric 95% confidence intervals.
- Change from baseline to week 16 in the CGI-C: the hypothesis of superiority of safinamide compared to placebo will be assessed using the Wilcoxon-Mann-Whitney test stratified by centre, whilst point estimate of treatment differences will be reported as Hodges-Lehmann estimators together with associated two-sided nonparametric 95% confidence intervals.
- Change from baseline to week 16 in the PDQ-39 score: the hypothesis of superiority of safinamide compared to placebo will be assessed using an ANCOVA model

parameterized as above, with point estimate of treatment differences reported as Least-Square Mean with associated two-tailed 95% confidence intervals and two-sided p-value.

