**Statistical Analysis**

All efficacy analyses will be performed on the Full Analysis Set (FAS) population. Analysis of the primary and secondary efficacy variables will be also carried out on the Per Protocol (PP) population to assess the robustness of the findings. Safety outcomes will be analysed on the Safety population.

The primary objective of the study is to evaluate the change from baseline to week 16 in the mean “OFF” time, as assessed by the 24-hour patient diary, of safinamide 100 mg/day compared to placebo, given as add-on therapy in PD patients with motor fluctuations on stable doses of L-dopa. The analysis of primary efficacy parameter will be done using an analysis of co-variance (ANCOVA) with treatment and centre as independent factor, baseline mean “OFF” time measurement as covariate and change from baseline as dependent variable. Results will be reported as Least-Square Means for treatment differences with associated two-tailed 95% confidence intervals and corresponding two-sided p-values.

The key secondary objective of the study is to evaluate the change from baseline to week 16 in pain severity, as assessed by an 11-point Numerical Rating Scale (NRS), of safinamide 100 mg/day compared to placebo. Exactly as for the analysis of the primary

endpoint, the analysis of key secondary efficacy parameter will be done using an analysis of co-variance (ANCOVA) with treatment and centre as independent factor, baseline NRS measurement as covariate and change from baseline as dependent variable. Results will be reported as Least-Square Means for treatment differences with associated two-tailed 95% confidence intervals and corresponding two-sided p-values.

The overall type I family-wise error rate for testing the primary endpoint and key secondary endpoint will be controlled at the two-tailed 0.05 significance level using a fixed sequence procedure. This procedure will be fully described in the protocol.

The same statistical approach (ANCOVA) will be taken for the analysis of change from baseline to week 16 of all the other supportive secondary end-points listed above with the exclusion of CGI-S and CGI-C scores which will be analysed using the Wilcoxon-Mann-Whitney test stratified by centre. For the analyses of supportive secondary efficacy end-points no adjustment of significance level will be made to account for multiple comparisons.

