### 9.2.1 Visit 2 - Baseline Visit (Week 0 / Day 1)

The following assessments and procedures will be performed as detailed in the Study Flow Chart ([Section 29.0, Appendix 1](#)):

- Check of inclusion and exclusion criteria (note: inclusion and exclusion criteria must be fulfilled before patient is randomized).
- Vital signs (pulse rate, systolic and diastolic blood pressure measured after at least 5 minutes in the supine position).
- Completion of UPDRS, PDQ-39 and CGI-S by the rater ([Section 10.1.6](#)).
- Completion of NRS by the patient (the night before the visit) ([Section 10.1.6](#)).
- Recording of prior medications, concomitant medications and therapies.
- Recording of AEs ([Section 17.0](#)).
- Review and evaluate daily diary ([Section 10.1.6](#)).
- Provide additional daily diary training, as required.
- Issue daily diary with instructions to be completed two days before the visit at week 2 (visit 3).
- Randomisation to study treatment.
- Following completion of the relevant assessments and procedures, patients will take their first 50 mg dose of oral safinamide or placebo at the study center.
- Dispense study medication (safinamide or placebo 50 mg od) for the next 14 days. Patients will take 50 mg/day safinamide at home in the morning for 2 weeks, then the dose will be increased at home to 100 mg/day the day after the Visit 3/week2, ideally at day 15. Safinamide can be taken with or without food.

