### **Clinical Global Impression (CGI)**

The CGI (22) is the general name for 2 scales, the CGI-Severity scale (CGI-S) and the CGI-Change scale (CGI-C). The CGI-S scale measures global severity of illness at a given point in time. It will be rated on a 7-point Likert-type scale ranging from 1 (normal, not ill at all) to 7 (extremely severe). The CGI-S will be assessed at all visits, starting at baseline. The CGI-C scale will measure the change in the patient's clinical status from baseline using a 7-point scale, ranging from 1 (very much improved) to 7 (very much worse), with a score of 4 indicating no change. The change from the patient's baseline condition will be assessed by the Investigator at all post-baseline visits. In completing the CGI-C, the rater will review all efficacy-related data, and assess its clinical meaningfulness.

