#### **20.4.4 Handling of missing data**

Missing data on the primary and key secondary efficacy endpoints will be imputed using multiple imputation (MI) as the primary imputation method and last observation carried forward (LOCF) as sensitivity analysis. Missing data on all the other secondary efficacy endpoints will be imputed only using LOCF method. Details regarding the multiple imputation approach (i.e. number of imputations, the randomization seed and the imputation and analysis models that will be used) will be reported in the SAP.

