#### **20.4.5 Multiplicity**

The overall type I family-wise error rate for testing the primary and the key secondary efficacy endpoints will be controlled at the two-sided 0.05 significance level using a Fixed Sequence Procedure (6). Following this procedure, progression to next step will only occurs as long as null hypothesis ( $H_0$ : Active effect = Vehicle effect) from previous step is rejected at 0.05 significance level. The testing procedure is stopped and all the remaining null hypotheses accepted if an acceptance occurs. All individual hypothesis tests will be 2 sided.

1. The first step will test the primary efficacy parameter. The p-value for the null hypothesis must be less than 0.05 to be considered to have met the primary efficacy objective. If the null hypotheses is not rejected (i.e., p-value  $>0.05$ ), the subsequent statistical test (second step) will not be considered statistically significant.
2. The second step will test the key secondary efficacy parameter “change from baseline to week 16 in pain severity, as assessed by an 11-point Numerical Rating Scale”.

For the analyses of supportive secondary efficacy end-points (not key) no adjustment of significance level will be made to account for multiple comparisons.

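### Optional gain on a supportive endpoint: the planned week-16 CGI-S test is valid but leaves out the baseline CGI-S that the trial collects

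*Protocol*

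**What the plan says.** In section 20.4.3.3 of the protocol the entry for CGI-S begins "CGI-S score assessed at week 16: the hypothesis of superiority of safinamide compared to placebo will be assessed using the Wilcoxon-Mann-Whitney test". The test is stratified by centre, and a Hodges-Lehmann estimate with a nonparametric 95% interval goes with it. The Summary (section 3.0) takes both CGI scales out of the baseline-adjusted ANCOVA used for the other secondary endpoints: "with the exclusion of CGI-S and CGI-C scores which will be analysed using the Wilcoxon-Mann-Whitney test stratified by centre".

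The baseline rating exists. Section 9.2.1 lists for Visit 2 "Completion of UPDRS, PDQ-39 and CGI-S by the rater", section 10.1.6 states "The CGI-S will be assessed at all visits, starting at baseline", and the flow chart agrees.

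CGI-C is different. Section 10.1.6 defines it as a 7-point rating of change since baseline, "ranging from 1 (very much improved) to 7 (very much worse), with a score of 4 indicating no change", made only after baseline. Sections 3.0, 20.2.2 and 20.4.3.3 nevertheless list it as a change from baseline to week 16.

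Both endpoints are analysed in the full analysis set ("The FAS will be used to produce summaries of baseline patient characteristics and for the analysis of all efficacy endpoints"), with LOCF for missing values ("Missing data on all the other secondary efficacy endpoints will be imputed only using LOCF method"). Both lie outside the fixed sequence ("For the analyses of supportive secondary efficacy end-points (not key) no adjustment of significance level will be made").

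**The concern.** CGI-S stands alone among the efficacy endpoints. OFF time, pain NRS, both ON-time measures, UPDRS total, part II and part III, and PDQ-39 all get an ANCOVA with the baseline value as covariate. CGI-S is the only endpoint that has a baseline measurement and a planned test that does not use it. The ordinal scale is a good reason for a rank test, but a rank test can also be adjusted for baseline.

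What is at stake is precision on one supportive comparison. If baseline and week-16 severity are clearly correlated, the planned test has less power than the collected data allow, and it makes no correction for a chance imbalance in baseline severity.

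**Working it through.** **Inputs from the protocol.** Allocation is 1:1, with 306 randomised (153 per arm), 260 evaluable (130 per arm), and about 35 centres, or roughly 306/35 = 8.7 patients per centre. CGI-S is analysed in the full analysis set with LOCF, so up to 153 per arm enter the test. Section 20.4.6 foresees pooling small sites into regions.

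**The plan's own figures.** The protocol gives none for CGI. Its sample-size figures reproduce:
- OFF time: pooled SD = sqrt((2.35² + 2.06²)/2) = 2.21, and a difference of 0.9 h with 130 per arm gives 90.5% power (90% stated).
- NRS: 98.0% alone. Jointly with the primary, assuming independence, 0.905 × 0.980 = 0.887 (88% stated).
- Randomised: 260/0.85 = 306.

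**Assumed inputs, because the protocol has no CGI figures.** Latent shift 0.25 SD; category probabilities 2/8/25/35/22/7/1%; baseline to week-16 correlation ρ of 0.3, 0.5 or 0.7; one stratum, 8 pooled regions (an assumed number) or 35 centres.

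**Validity.** Re-randomising 306 patients over 35 centres, the planned test rejects a true null in 5.3% of 30,000 draws (Monte Carlo SE 0.1 points). It holds its level.

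**Why adjustment can help.** On the latent scale the residual variance falls to 1 − ρ² of its unadjusted value: 0.91, 0.75 and 0.51 at ρ = 0.3, 0.5 and 0.7.

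**Power with no centre effect, 153 per arm.** 10,000 runs per setting; the planned test is van Elteren, and the adjusted test uses week-16 ridits residualised on baseline ridits. Cells give planned → adjusted, in %.

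| Strata | ρ = 0.3 | ρ = 0.5 | ρ = 0.7 |
|---|---|---|---|
| 1 | 53.8 → 57.2 | 54.5 → 64.6 | 54.6 → 76.9 |
| 8 | 52.9 → 56.2 | 52.9 → 63.0 | 52.5 → 74.2 |
| 35 | 47.7 → 50.2 | 48.1 → 56.3 | 47.6 → 67.8 |

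The gains are about 2.5 to 3.5, 8 to 10 and 20 to 22 points. With 130 per arm they are about 2 to 2.5, 7 to 9 and 18 to 22.

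**Power with a shared centre component.** Suppose 15% of the variance is a centre or rater level present at both visits, inside the same overall ρ. Stratification already removes it. The correlation left within centres is (ρ − 0.15)/0.85:
- ρ = 0.3: 0.15/0.85 = 0.18, residual variance 1 − 0.18² = 0.97
- ρ = 0.5: 0.35/0.85 = 0.41, residual variance 1 − 0.41² = 0.83
- ρ = 0.7: 0.55/0.85 = 0.65, residual variance 1 − 0.65² = 0.58

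Simulated with ranking and adjustment both done within centre, the gains shrink to about 0 to 0.5, 5 and 16 points. Type I error stays at about 5%, and no power is lost.

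**Why not a change score.** Its variance relative to the week-16 score is 2(1 − ρ): 1.4, 1.0 and 0.6. It loses whenever ρ is below about 0.5. In a separate simulation (latent shift 0.3 SD, 35 centres, 306 patients, ρ = 0.3, 600 runs) power was 47% for the change score and 62% for the planned test.

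**CGI-C.** No baseline CGI-C exists to subtract. Subtracting the no-change value of 4 from every patient leaves all ranks, the Wilcoxon p-value and the Hodges-Lehmann difference as they were.

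**The case against.** The strongest reply is that nothing here is wrong. The protocol says the same thing about CGI-S wherever it appears, the test holds its level, and the endpoint is supportive. CGI-C already gives a global comparison referenced to baseline. The statistical analysis plan, which is not shown, could add an adjusted analysis. All of this stands, and keeping the planned test would be defensible. It limits the point to an optional improvement.

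A second reply is that the gain depends on the correlation arising within centres. The same rater should assess a patient throughout (section 10.1.6), so part of the correlation is probably centre or rater level, which stratification already removes. That also stands, and it is why the range starts near zero. It has been argued further that adjustment could cost power: with a 15% centre component and ρ = 0.3, one set of simulations showed changes of about −2 to 0 points. Those losses do not appear when the ranks and the covariate adjustment are both formed within centre, so the fix has to specify this.

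A third reply is that an adjusted p-value beside an unadjusted interval invites conflict. This is a real cost and is counted under the fix.

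A reader might infer that ignoring baseline biases the CGI-S comparison or inflates its error rate. Randomisation and the simulated type I error rule that out. A reader might also infer that the CGI-C endpoint cannot be computed as defined. The description of the scale leaves only one reading, the week-16 rating, and the Summary already speaks of CGI-S and CGI-C scores.

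**Conclusion.** The point holds as a low-cost improvement, not as an error. The planned CGI-S test is valid and loses only precision.

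Assuming a 0.25 SD latent shift, the category probabilities above and 153 per arm, adjustment is worth about 0 to 3 points of power at ρ = 0.3, 5 to 10 at 0.5 and 16 to 22 at 0.7. The lower ends go with an assumed 15% shared centre component, the upper ends with none. The protocol gives no information on where in this range the trial lies, so a material gain cannot be promised.

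The primary and key secondary results, the sample size and the fixed sequence are untouched. The CGI-C wording is editorial.

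**What to change.** **CGI-S (optional), sections 3.0 and 20.4.3.3.**
- Keep the week-16 score as the endpoint.
- Name as its test a rank ANCOVA stratified by centre, or by pooled region if sites are pooled under section 20.4.6. Rank week-16 and baseline CGI-S within stratum and use the baseline rank as covariate.
- Keep the Hodges-Lehmann estimate and interval, labelled as an unadjusted description.
- Do not use a plain change score.
- Settle this before unblinding.

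**Cost.** No new data, visits or patients are needed. The price is that the interval no longer matches the test. Under the assumptions above without a centre effect and with 153 per arm, the unadjusted and adjusted verdicts at 0.05 differ in about 9%, 16 to 17% and 27% of trials at ρ = 0.3, 0.5 and 0.7. In about 3 to 4% of trials only the unadjusted test is significant. The text must therefore say which analysis is the test.

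**CGI-C (editorial), sections 3.0, 20.2.2 and 20.4.3.3.** Write *CGI-C score at week 16*. The planned test and estimate stay as they are.
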